# Clinical Study Protocol

## Johnson & Johnson Vision Care, Inc.

Table 11: Power Calculations of NIBUT for N=54

Effect size ( $\Delta$ )	Common standard deviation ( $\sigma$ )		
	3	4	5
-2.1	81%	60%	45%
-1.1	38%	26%	20%
0.0	5%	5%	5%

The sample size is sufficiently large to demonstrate lower NIBUT with ~80% power to Symptomatic subjects if  $\Delta \leq -2.1$  and  $\sigma \leq 3$ .

3. Hypothesis 3: Symptomatic subjects will have, on average, lower TMH compared to asymptomatic subjects after 14 hours of lens wear.

Table 12: Power Calculations of TMH for N=54

Effect size ( $\Delta$ )	Common standard deviation ( $\sigma$ )		
	0.04	0.06	0.08
-0.04	98%	78%	56%
-0.03	86%	57%	39%
-0.01	23%	15%	12%

The sample size is sufficiently large to demonstrate lower TMH with ~80% power to Symptomatic subjects if  $\Delta \leq -0.03$  and  $\sigma < 0.06$ .

4. Hypothesis 4: Symptomatic subjects will have, on average, greater tear film osmolarity (TOSM) compared to asymptomatic subjects after 14 hours of lens wear.

Table 13: Power Calculations of TOSM for N=54

Effect size ( $\Delta$ )	Common standard deviation ( $\sigma$ )		
	20	25	30
10	57%	42%	33%
12	70%	54%	42%
14	81%	65%	52%

The sample size is sufficiently large to demonstrate greater TOSM with ~80% power to Symptomatic subjects if  $\Delta \geq 14$  and  $\sigma \leq 20$ .

5. Hypothesis 5: Symptomatic subjects will have, on average, greater mean number of white blood cells (WBC) (visualized by confocal microscopy) in both the upper and lower lid margins compared to asymptomatic subjects after 6 hours of lens wear.

Table 14: Power Calculations of WBC for N=54

Mean ratio ( $\phi$ )	Common coefficient of variances (CV)		
	0.65	1.0	1.3
1.0	5%	5%	5%

# Clinical Study Protocol

## Johnson & Johnson Vision Care, Inc.

1.5	80%	55%	43%
2.0	100%	92%	81%

The sample size is sufficiently large to demonstrate greater WBC with ~80% power to Symptomatic subjects if  $\phi \geq 1.5$  and  $CV \leq 0.65$ ; and  $\phi \geq 2$  and  $CV \leq 1.3$ .

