### **14.2. Sample Size Justification**

The sample size was not determined by any empirical power calculation. The plan is to enroll approximately 210-240 subjects with a completion target of 27 subjects per strata (Symptomatic and Asymptomatic). Assuming a sample of size 27 subjects per strata, the statistical power was calculated using SAS procedure PROC POWER. The goal is to show Symptomatic subjects have, on average, lower Non-invasive tear Breaks up Time (NIBUT) and Tear Meniscus Height (TMH); and greater Lid Margin Staining (LMS), Tear Film Osmolarity (OSM), and White Blood Cell (WBC) count compared to Asymptomatic subjects.

Table 4 contains the information of two previous studies and their corresponding subject disposition. Tables 5 to Table 9 below summarizes the primary endpoints from the studies [REDACTED] and [REDACTED] that are corresponded to the current study and therefore used to compute the power.

Table 4: Historical Studies Included

Study	Study Design	Endpoints Collected	No. of Enrolled	No. of Completed - Asymptomatic	No. of Completed - Symptomatic
[REDACTED]	Cross-sectional study of subjects wearing Dailies AquaComfort Plus	Lid Margin Staining, NIBUT, TMH, Tear film osmolarity,	42	25	16
[REDACTED]	Cross-sectional study of subjects	Lid Margin Staining,	74	27	15

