# Clinical Study Protocol

## Johnson & Johnson Vision Care, Inc.

Table 9: Mean White Bloods Cell (WBC) Count (Confocal Microscopy) – Completed Per-Protocol Population [REDACTED]

Mean[STD]	Eyelid	Strata/Eye			
		Asymptomatic N=27		Symptomatic N=15	
		Left	Right	Left	Right
Visit 2 (2-14 Days after Visit 1)	Lower	3.044 (2.7755)	4.062 (4.8873)	6.175 (5.8041)	6.533 (4.1495)
	Upper	3.006 (3.1092)	4.130 (3.9155)	6.277 (6.8528)	5.633 (5.5359)
Visit 3 (2-14 Days after Visit 2)	Lower	2.957 (2.8150)	3.790 (4.7627)	4.444 (4.7879)	6.555 (6.6327)
	Upper	3.197 (3.8542)	4.253 (4.0071)	8.267 (10.5946)	9.301 (10.8690)

N=Number of Subjects [REDACTED]

The power calculation of LMS, NIBUT, TMH, and TOSM were conducted for the combination of the different effect sizes ( $\Delta$  = Symptomatic – Asymptomatic) and the different common variances ( $\sigma$ ). The power calculation of WBC was conducted for the combination of the different mean ratios ( $\phi$  =Symptomatic/Asymptomatic) and the different common coefficient of variances (CV). CV, also known as the relative standard deviation, is the ratio of the standard deviation to the mean.

The parameters  $\Delta$ ,  $\sigma$ ,  $\phi$ , and  $CV$  were estimated from the data of [REDACTED] and [REDACTED]. Historical data suggest that increasing the effect sizes or the mean ratios and decreasing the standard deviation or the coefficient of variations increases the power. For the fixed number of 27 subjects per strata, the criteria that need to be satisfied in order to obtain ~80% power corresponding to the primary hypotheses are presented below in Table 10 to Table 14:

1. Hypothesis 1: Symptomatic subjects will have, on average, greater upper and lower lid margin staining (LMS) compared to asymptomatic subjects after 14 hours of lens wear.

Table 10: Power Calculations of LMS for N=54

Effect size ( $\Delta$ )	Common standard deviation ( $\sigma$ )		
	0.5	0.7	0.9
0.30	70%	46%	33%
0.35	81%	57%	41%
0.40	90%	67%	49%

The sample size is sufficiently large to demonstrate greater LMS with ~80% power to Symptomatic subjects if  $\Delta \geq 0.35$  and  $\sigma \leq 0.5$ .

2. Hypothesis 2: Symptomatic subjects will have, on average, shorter NIBUT compared to asymptomatic subjects after 14 hours of lens wear.

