### 14.4. Level of Statistical Significance

Each pre-planned primary and secondary hypothesis will be analyzed with a two-sided type I error rate of 5%.

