# Clinical Study Protocol

## Johnson & Johnson Vision Care, Inc.

- Unstructured Covariance Structure (UN)
- Homogenous Compound symmetry (CS)

The structure that returns the lowest Akaike Information Criteria Corrected (AICC) will be selected as the structure that best fit the data. Heterogeneous covariance structures across strata may be considered if necessary. The Kenward and Roger method (Kenward and Roger, 1997) will be used for the denominator degree of freedom.

The Comparison between the symptomatic and the asymptomatic strata will be carried out using one-sided 95% confidence intervals for the Least-squares means risk ratio (symptomatic over asymptomatic) at 6-hour follow up for the hypothesis given below:

$$\begin{aligned} H_0: \mu_S / \mu_A &\leq 1 \\ H_A: \mu_S / \mu_A &> 1, \end{aligned}$$

where S=Symptomatic and A=Asymptomatic. Adjustments for multiple comparisons across lower and upper lid margins will be performed using a simulation method with alpha equal to 0.05 (Edwards and Berry, 1987). A statistically significantly greater density of WBC, on average, in both the upper and lower lid margins for symptomatic subjects compared to asymptomatic subjects after 6 hours of lens wear will be concluded if the multiple adjusted lower limit of the 95% confidence intervals for the Least-squares means risk ratio is above 1.0.

**Remark:** For all the above models, the Kenward and Roger method implemented with the *kr2* option in SAS will be used for the calculation of the denominator degrees of freedom. Heterogenous models across subject strata may be considered. The log-likelihood ratio test will be used to test for homogeneity between the two strata. Convergence limitations will be taken into account as necessary. If convergence is problematic, then reduced versions of the corresponding model will be considered. When the normality assumption does not hold for an endpoint, the analysis will be conducted on transformed data; generalized linear models or generalized linear mixed models with appropriate distributions will also be considered on the original data.

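### Table 14's ~80% WBC power is for one lid comparison; Hypothesis 5 needs both lids with adjusted limits, which at ratio 1.5, CV 0.65 gives roughly 48–65% (lid correlation 0–0.8 assumed)

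*Combined protocol and SAP*

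**What the plan says.** Section 14.2 presents Tables 10 to 14 as the conditions under which about 80% power is reached for the primary hypotheses. "Assuming a sample of size 27 subjects per strata, the statistical power was calculated using SAS procedure PROC POWER". It also states that the sample size did not come from a power calculation.

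**WBC.** The text under Table 14 reads "The sample size is sufficiently large to demonstrate greater WBC with ~80% power to Symptomatic subjects if" the ratio is at least 1.5 and CV at most 0.65, or the ratio is at least 2 and CV at most 1.3. Hypothesis 5, printed just above that table, claims a higher count "in both the upper and lower lid margins compared to asymptomatic subjects after 6 hours of lens wear". Section 14.5 tests it with "one-sided 95% confidence intervals for the Least-squares means risk ratio (symptomatic over asymptomatic) at 6-hour follow up" and adds: "Adjustments for multiple comparisons across lower and upper lid margins will be performed using a simulation method with alpha equal to 0.05". Its decision rule says that greater density "in both the upper and lower lid margins for symptomatic subjects compared to asymptomatic subjects after 6 hours of lens wear will be concluded if" one condition is met: an adjusted lower limit for the ratio above 1.

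**LMS.** The text under Table 10 reads "The sample size is sufficiently large to demonstrate greater LMS with ~80% power to Symptomatic subjects if" the difference is at least 0.35 and the SD at most 0.5. Hypothesis 1 names upper and lower lids. Section 14.5 gives two models, both adjusted for baseline: Model-1 by lid, with adjustment across lids, and Model-2 on the average of the two lids. It does not say which one decides.

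**The concern.** Power is a property of a decision rule. Table 14 has a single ratio and a single CV: no second lid, no correlation between lids, no multiplicity adjustment. The WBC rule has all three. A rule that needs two successes is harder to meet than either test alone, and adjusted limits make each success harder still. The printed figure is therefore too high for Hypothesis 5 at the conditions the plan names.

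The introduction says the study is meant to confirm earlier findings and pick the best endpoints for predicting end-of-day discomfort. If WBC misses the both-lid rule, a reader who believes the design had 80% power would count that miss too heavily against the endpoint.

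For LMS the difficulty comes one step earlier: until the deciding model is named, the reader cannot tell which claim Table 10's power belongs to.

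**Working it through.** **Inputs.** 27 subjects per stratum (14.2), so 52 degrees of freedom and √(27/2) = 3.674. One-sided 5% (14.5), critical t = 1.675. Ratios and CVs from Table 14; differences and SDs from Tables 5 and 10. The between-lid correlation ρ is not in the documents; I assume 0 to 0.8.

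**1. Reproduce Table 14.** Log-scale SD = √ln(1 + CV²); noncentrality = ln(ratio) / log-SD × 3.674; power from the noncentral t.
- Ratio 1.5, CV 0.65: log-SD 0.594, noncentrality 2.51, power 79.7% (printed 80%).
- Ratio 2, CV 1.3: log-SD 0.995, noncentrality 2.56, power 81.1% (printed 81%).

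All nine cells of Table 14, and all nine of Table 10, agree within 2 points. At two-sided 5% the two WBC cells would be 69.3% and 71.0%, so the tables are one-sided single-comparison powers.

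**2. Require both lids.** At ρ = 0 the joint power is the product: 0.797² = 0.635 and 0.811² = 0.658. For ρ > 0, I simulated correlated pairs of t-statistics with the same effect in each lid.

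**3. Add the planned adjustment.** The one-sided critical value for the larger of two t-statistics is about 2.00, 1.96 and 1.89 at ρ = 0, 0.5 and 0.8. At ρ = 0, per-lid power falls to 69.6%, and 0.696² = 0.484.

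| Condition | ρ | One lid (as printed) | Both lids, unadjusted | Both lids, adjusted |
|---|---|---|---|---|
| Ratio 1.5, CV 0.65 | 0 | 80% | 64% | 48% |
| | 0.5 | 80% | 68% | 56% |
| | 0.8 | 80% | 72% | 65% |
| Ratio 2, CV 1.3 | 0 | 81% | 66% | 51% |
| | 0.5 | 81% | 70% | 59% |
| | 0.8 | 81% | 74% | 67% |

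A bivariate normal approximation moves these by about one point.

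**4. LMS, if the lid average decides (Model-2).** The 14-hour differences in Table 5 are 1.31 − 0.74 = 0.57 (upper) and 1.47 − 1.34 = 0.13 (lower). Their mean is 0.35, Table 10's middle effect. Pooled SDs, weighted by 50 and 32 eyes, are 0.882 (upper) and 0.751 (lower). SD of the average = √(0.882² + 0.751² + 2ρ × 0.882 × 0.751) / 2.

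| ρ | SD of average | Power at 0.35 | Baseline correlation giving residual SD 0.5 |
|---|---|---|---|
| 0 | 0.58 | 71% | 0.51 |
| 0.5 | 0.71 | 56% | 0.71 |
| 0.8 | 0.78 | 50% | 0.76 |

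The last column solves SD × √(1 − r²) = 0.5. At the stated condition itself (0.35, 0.5), power is 81.4%, as printed.

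**5. LMS, if both lids are required (Model-1).** At 0.35 and 0.5 in each lid, power for ρ = 0, 0.5, 0.8 is 66%, 71%, 75% unadjusted and 51%, 59%, 67% adjusted. At the Table 5 lower-lid difference the noncentrality is 0.13 / 0.751 × 3.674 = 0.64, and the lower lid alone has 15.5% power before any baseline gain.

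**The case against.** **The tables contain no error, and the plan promises little.** Every cell checked reproduces, the sample size is openly not power-based, and ~80% is conditional on stated effect and spread. All of that stands. But the text ties the condition to Hypothesis 5, and meeting it does not give about 80% power for Hypothesis 5.

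**The size depends on an unknown correlation and on threshold cells.** This also stands. At ρ = 0.99 and ratio 1.5, CV 0.65, both-lid power is 78% unadjusted and 76% adjusted. At ratio 2, CV 1.0 it is about 84–88% unadjusted and 73–83% adjusted for ρ from 0 to 0.8. The shortfall is at the conditions the plan names, not everywhere in the table.

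**A stronger reading for LMS is tempting but not supported.** A reader might infer that the plan claims 80% power for LMS while the design has at most about 16%, because a both-lid rule at Table 5 values gives 12–16% unadjusted.
- The plan never claims 80% at Table 5 values.
- Model-2 tests the lid average, section 2.2 defines a final grade as that average, and Table 10's 0.35 matches it.
- The contrast changes the rule, the effect and the SD together; most of the drop comes from the lower-lid difference of 0.13.
- Both models adjust for baseline. With assumed baseline correlations of 0.5, 0.7 and 0.8, lower-lid power is about 18%, 22% and 27%: still low, but 16% is not a ceiling.

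Nor does an SD of 0.5 contradict Table 5. Without covariates it would need a negative lid correlation (about −0.26), but baseline adjustment could also deliver it. Table 10 already prints 57% and 41% at SDs of 0.7 and 0.9.

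**Conclusion.** The point holds for WBC. The ~80% attached to Hypothesis 5 is per-lid power at one-sided 5%. Under the rule in 14.5, at the two conditions the plan names, power is about 64–74% before the lid adjustment and 48–67% with it. This assumes equal effects in both lids, a between-lid correlation of 0 to 0.8, and Table 14's own ratio test in place of the planned Poisson mixed model.

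For LMS the supported conclusion is narrower: the plan does not say which model decides Hypothesis 1, so Table 10's power has no defined claim. If the average decides, σ ≤ 0.5 relies on a gain from the baseline covariate that the plan does not state. If both lids are required, ~80% is too high even at the stated condition. The documents do not support a headline that LMS power is 16%.

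Separately, 14.4 says "Each pre-planned primary and secondary hypothesis will be analyzed with a two-sided type I error rate of 5" percent, whereas 14.5 and the power tables are one-sided. The figures here follow 14.5.

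**What to change.** In section 14.2:
1. Label Table 14 as power for one lid. Beside it, give power for the both-lid rule with the adjusted limits, over a stated range of between-lid correlation, and reword the ~80% sentence to match.
2. State whether Model-1 or Model-2 decides Hypothesis 1, and label Table 10 accordingly.
   - If Model-2: say that Table 5 implies an average-lid SD of about 0.58–0.78 and power of about 71% down to 50% before baseline adjustment, and state the baseline correlation on which σ ≤ 0.5 relies.
   - If Model-1 with both lids required: give both-lid power at 0.35 and 0.5 (about 66–75% unadjusted, 51–67% adjusted), and note that it is much lower at the Table 5 lower-lid difference of 0.13.

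The cost is a few recalculated figures and some wording. The printed power becomes less favourable; no subjects, visits or measurements are added.

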### 14.3. Analysis Populations

#### **Safety Population:**

All subjects who were administered any test article excluding subjects who drop out prior to administering any test article. At least one observation should be recorded.

#### **Per-Protocol Population:**

All subjects who have successfully completed all visits and did not substantially deviate from the protocol as determined by the trial cohort review committee prior to database hard lock (Per-Protocol Population). Justification of excluding subjects with protocol deviations in the per-protocol population set will be documented in a memo to file.

#### **Intent-to-Treat (ITT) Population:**

All randomized subjects regardless of actual treatment and subsequent withdrawal from study or deviation from protocol. At least one observation should be recorded.

### 14.4. Level of Statistical Significance

Each pre-planned primary and secondary hypothesis will be analyzed with a two-sided type I error rate of 5%.

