# Clinical Study Protocol

## Johnson & Johnson Vision Care, Inc.

Comparisons between subject strata for LMS will be carried out using a one-sided 95% CI of least-square means differences (symptomatic - asymptomatic) at 14-hour follow-up for the hypothesis given below:

$$H_0: \mu_S - \mu_A \leq 0$$
$$H_A: \mu_S - \mu_A > 0,$$

where S=Symptomatic and A=Asymptomatic. For only model-1, adjustments for multiple comparisons across lower and upper eyelids' will be performed using a simulation method with alpha equal to 0.05 (Edwards and Berry, 1987). A statistically greater upper and lower LMS, on average, for symptomatic subjects compared to asymptomatic subjects after 14 hours of lens wear will be concluded if the lower limit of the 95% confidence intervals for the least-squares means is greater than 0.

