### **Non-invasive tear break-up time (NIBUT) and Tear Meniscus Height (TMH)**

NIBUT and TMH will be analyzed using a linear mixed model separately by adjusting the baseline as a covariate. The model will include subject strata (asymptomatic/symptomatic), time event (i.e., fitting and 14-hours follow-up), and strata by time event interaction as fixed effects; subject will be included as random effects (G-side). Other characteristics such as age, gender, and race will be included as fixed covariates when appropriate. Different covariance structures will be considered to model the residual errors between the repeated measurements within time event from the same subject (R-side). The covariance structure will be selected based on the finite-sample corrected Akaike's Information Criterion. The following covariate structures will be considered:

- Unstructured Covariance Structure (UN)
- Homogenous Compound symmetry (CS)
- Heterogeneous Compound Symmetry (CSH)
- Spatial Power (SP[POW])

For SP(POW) covariance structure, subject and time event within subject will be included as random effects. For the remaining structures, only subject will be included as a random effect. The structure that returns the lowest Akaike Information Criteria Corrected (AICC) will be selected as the structure that best fit the data. Heterogeneous covariance structures across strata may be considered if necessary. The Kenward and Roger method (Kenward and Roger, 1997) will be used for the denominator degree of freedom.

Comparisons between subject strata for NIBUT and TMH will be carried out using a one-sided 95% CI of least-square means differences (symptomatic - asymptomatic) at 14-hour follow-up for the hypothesis given below:

$$H_0: \mu_S - \mu_A \geq 0$$
$$H_A: \mu_S - \mu_A < 0.$$

where S=Symptomatic and A=Asymptomatic. No multiple adjustment will be necessary since the hypothesis test will be conducted based on only 14-hour follow-up. A statistically shorter

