### **Tear Film Osmolarity (TOSM)**

TOSM will be analyzed using a linear mixed model by adjusting the baseline TOSM as a covariate. The model will include subject strata (asymptomatic/symptomatic), time event (i.e., fitting and 14-hours follow-up), and strata by time event interaction as fixed effects; subject will be included as random effects (G-side). Other characteristics such as age, gender, and race will be included as fixed covariates when appropriate. Different covariance structures will be considered to model the residual errors between the repeated measurements within time event from the same subject (R-side). The covariance structure will be selected based on the finite-sample corrected Akaike's Information Criterion. The following covariate structures will be considered:

- Unstructured Covariance Structure (UN)
- Homogenous Compound symmetry (CS)

The structure that returns the lowest Akaike Information Criteria Corrected (AICC) will be selected as the structure that best fit the data. Heterogeneous covariance structures across strata may be considered if necessary. The Kenward and Roger method (Kenward and Roger, 1997) will be used for the denominator degree of freedom.

Comparisons between subject groups for TOSM will be carried out using a one-sided 95% CI of least-square means differences (symptomatic - asymptomatic) at 14-hour follow-up for the hypothesis given below:

$$\begin{aligned} H_0: \mu_S - \mu_A &\leq 0 \\ H_A: \mu_S - \mu_A &> 0, \end{aligned}$$

where S=Symptomatic and A=Asymptomatic. No multiple adjustment will be necessary since the hypothesis test will be conducted based on only 14-hour follow-up. A statistically greater TOSM, on average, for symptomatic subjects compared to asymptomatic subjects after 14 hours of lens wear will be concluded if the lower limit of the 95% confidence intervals for the Least-squares means is greater than 0.

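### Section 14.4 sets a two-sided 5% error rate for every primary hypothesis, but Section 14.5 tests each one-sided at 5% and Tables 10-14 match only that; at the stated alpha the ~80% power is about 70%.

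*Combined protocol and SAP*

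**What the plan says.** Section 14.4 (Level of Statistical Significance) is one sentence: "Each pre-planned primary and secondary hypothesis will be analyzed with a two-sided type I error rate of 5" per cent. It names primary hypotheses explicitly.

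Section 14.5 (Primary Analysis) writes directional hypotheses for all five measures and prescribes a one-sided interval for each:

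- Lid margin staining (LMS): "Comparisons between subject strata for LMS will be carried out using a one-sided 95% CI of least-square means differences".
- NIBUT and tear meniscus height (TMH): "Comparisons between subject strata for NIBUT and TMH will be carried out using a one-sided 95% CI of least-square means differences".
- Tear film osmolarity (TOSM): "Comparisons between subject groups for TOSM will be carried out using a one-sided 95% CI of least-square means differences".
- White blood cells (WBC): "using one-sided 95% confidence intervals for the Least-squares means risk ratio (symptomatic over asymptomatic) at 6-hour follow up".

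The sentences that define success then refer only to the upper or lower limit of the 95% confidence intervals, without repeating the sidedness. The secondary analysis in Section 14.6 uses two-sided 95% intervals, in line with 14.4.

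Section 14.2 takes 27 subjects per stratum, names PROC POWER, and gives power in Tables 10-14 without an alpha or a sidedness. Each table is followed by a conclusion of the form "The sample size is sufficiently large to demonstrate greater LMS with ~80% power to Symptomatic subjects", subject to stated limits on the effect size and the standard deviation (or, for WBC, the mean ratio and the coefficient of variation).

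**The concern.** A two-sided 5% test puts 2.5% in the hypothesised direction; a one-sided 95% limit puts 5% there. The two sections therefore give different critical values for the same primary comparisons. Any result with a directional p-value between 0.025 and 0.05 is a success under 14.5 and a failure under 14.4. Because the success sentences mention only a 95% interval, either version could be programmed, and the choice could be made after the data are seen.

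The power statements are affected as well. If the tables were built on the one-sided rule, a reader who applies the significance level in 14.4 will believe that the study has more power than it does. The study sets out to confirm and replicate earlier findings and to support a later meta-analysis, so the criterion for a positive finding needs to be fixed in advance.

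**Working it through.** **Inputs.** From Section 14.2: n = 27 per stratum, and the effect sizes, standard deviations, mean ratios and CVs in Tables 10-14. From 14.4: alpha 0.05, two-sided. From 14.5: one-sided 95% limit, that is alpha 0.05, one-sided.

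**Method.** Two-sample pooled t-test, df = 2 × 27 − 2 = 52, with noncentrality

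λ = |Δ| / (σ × √(2/27)), where √(2/27) = 0.2722.

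For WBC, Δ is ln(φ) and σ is √(ln(1 + CV²)). Power is the probability that a noncentral t with 52 df exceeds the critical value: 1.675 for one-sided 5% and 2.007 for two-sided 5%. The two-sided calculation also adds the opposite tail, which is negligible here.

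**Noncentralities at the conditions of interest.**

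- LMS: 0.35 / (0.5 × 0.2722) = 2.572. NIBUT (2.1/3) and TOSM (14/20) have the same standardised effect, 0.70, so the same λ.
- TMH at −0.04, SD 0.06: 0.04 / (0.06 × 0.2722) = 2.449.
- WBC at ratio 1.5, CV 0.65: ln 1.5 = 0.4055, σ = 0.5936, λ = 2.510.
- WBC at ratio 2.0, CV 1.3: ln 2 = 0.6931, σ = 0.9948, λ = 2.560.

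**Results.**

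| Measure and condition | Printed | One-sided 5% | Two-sided 5% |
|---|---|---|---|
| LMS, 0.35, SD 0.5 | 81% | 81.4% | 71.4% |
| NIBUT, −2.1, SD 3 | 81% | 81.4% | 71.4% |
| TOSM, 14, SD 20 | 81% | 81.4% | 71.4% |
| WBC, ratio 1.5, CV 0.65 | 80% | 79.7% | 69.3% |
| WBC, ratio 2.0, CV 1.3 | 81% | 81.1% | 71.0% |
| TMH, −0.04, SD 0.06 | 78% | 78.0% | 67.2% |
| TMH, −0.03, SD 0.04 | 86% | 85.9% | 77.2% |
| TMH, −0.03, SD 0.06 | 57% | 56.7% | 43.8% |

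**All cells.** The five tables hold 5 × 9 = 45 cells. One-sided 5% matches every one to within 1 point. Six are null cells (Δ = 0 or ratio 1) that read 5% under either rule and so cannot discriminate. Of the other 39, none rounds to its printed value at two-sided 5%. The tables were therefore almost certainly produced one-sided, although Section 14.2 does not say so.

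**Size in subjects.** At the LMS, NIBUT and TOSM conditions, 80% power at two-sided 5% takes 34 per stratum by the same calculation, against the planned 27.

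**The case against.** The strongest reply is that the tables contain no arithmetic error. Tables 10-14, the directional hypotheses in Section 2.3 and every primary-analysis subsection of 14.5 agree with each other; the outlier is one general sentence in 14.4. On that reading one-sided 5% was intended, and power is as printed. This stands as far as it goes: the loss to about 70% arises only if 14.4 governs. It does not remove the contradiction, because 14.4 names primary hypotheses and the plan uses the two-sided term deliberately in 14.6.

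Other points narrow the claim:

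- The one-sided basis of the tables is inferred from reproduction, not stated.
- TMH fits "about 70%" less well. Its printed condition is Δ ≤ −0.03 with SD below 0.06. The 78% cell sits at SD exactly 0.06, outside that condition, while the tabulated cell inside it goes from 86% to 77%. The condition is loose even on the plan's own table, which shows 57% at −0.03 and SD 0.06.
- LMS Model-1 and WBC carry a simulation-based adjustment across the two lids. There the doubling from 2.5% to 5% applies to the adjusted pair, not to each lid.
- The plan says that the sample size was not set by a power calculation, and the tables are simple two-group calculations, whereas the analyses are baseline-adjusted linear or mixed models and a Poisson mixed model. Neither 81% nor 71% is exactly the power of the planned test.

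The stand-alone SAP promised before database lock could settle the matter, but Section 14.10 says the analysis follows the protocol sections, which conflict.

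**Conclusion.** The concern holds: the text is wrong as written and must be corrected. Sections 14.4 and 14.5 give incompatible decision rules for all five primary measures. The one-sided rule doubles the permitted false-positive rate in the claimed direction from 2.5% to 5% per primary test (for LMS Model-1 and WBC, per lid-adjusted family), and 14.5 has no adjustment across the five measures to absorb this.

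At the significance level in 14.4, the conditions described as giving about 80% power give 69% to 71% for LMS, NIBUT, TOSM and WBC, and the 78% cell for TMH gives 67%. These figures assume 27 completers per stratum, a pooled t-test, and a lognormal ratio test for WBC, the set-up that reproduces the plan's own tables. The contradiction in the decision rule does not depend on those assumptions.

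**What to change.** Choose one rule and state it in the same terms in 14.2, 14.4 and 14.5.

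- **If 14.4 is to stand:** replace each one-sided 95% interval in 14.5 with a two-sided 95% interval, keep the directional reading of its upper or lower limit, and re-run Tables 10-14 with SIDES=2. Restate the power at the listed conditions as about 70%, giving the TMH figures cell by cell.
- **If one-sided 5% is intended:** amend 14.4 to say so for the primary hypotheses, keeping two-sided 5% for the secondary ones. The tables then stand.

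Under either route, add alpha and sidedness to 14.2 and to the success sentences in 14.5. Section 14.7 applies the primary procedure to Part 2 and also uses a one-sided 95% interval for change from baseline, so check it for consistency.

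The cost is wording and, under the first route, one PROC POWER re-run. Stated power becomes about 10 points less favourable. No extra subjects are needed, since the plan does not derive its sample size from these figures.
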